7.4 Number of subjects

A total of 40 patients will be included: 20 patients randomly assigned to a very low-calorie-ketogenic diet (VLCK diet group) and 20 patients randomly assigned to low calorie diet (control group).

7.5 Rationale of sample size

Exploratory pilot study to test a concept, where it has been estimated that 20 patients per group will be sufficient to analyze results.

7.6 Recruitment period

We expect a 4-month recruitment period

7.7 Criteria for withdrawal or dropouts

Patients who do not attend the control visits and/or have not undergone at least two MRIs (baseline and control after the end of ketosis or at month 6) will be considered as dropouts.

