9 STUDY PROCEDURES AND OUTCOME MEASURES

9.1 Outcome measures

9.1.1 *Primary variables*

- Liver fatty infiltration, measured by a MRI technique of fat liver quantification (Ideal IQ**).
- Visceral fat, measured by the area in squared centimeters at the level of the 3rd vertebrae, using MRI technique.

9.1.2 *Secondary variable*

- Liver stiffness detected by MR Elastography
- Adrenal gland linear measurement
- Body weight
- Salivary cortisol levels

9.1.3 *End points*

- Reduction of fat infiltration into the liver between the baseline visit and 2 months (or end of the ketosis stage) and between the baseline visit and the control visit at month 6 of treatment.
- Visceral fat reduction between the baseline visit and 2 months (or end of the ketosis stage) and between the baseline visit and the control visit at month 6 of treatment.
- Correlation between degree of liver fat infiltration and liver stiffness
- Correlation between adrenal gland size and BMI, visceral fat and liver steatosis.
- Correlation between salivary cortisol levels and BMI, visceral fat and liver steatosis.
- Weight loss between the baseline visit and 2 months (or end of the ketosis stage) and between the baseline visit and the control visit at month 6 of treatment.

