9.2 Study procedures

9.2.1 *Follow-up of patients*

The patient follow-up will be 6 months. The patients will be visited monthly and data will be recorded on 4 occasions: pre-inclusion, baseline visit, final visit Active stage (end of ketosis) and visit at month 6.

Patients will be included after verifying the inclusion and exclusion criteria and after obtaining the signed informed consent.

Screening visit (day -15). In this visit, the patient's medical history will be assessed and a complete blood test will be required to verify the inclusion/exclusion criteria: complete blood count (red blood cells, leukocytes, neutrophils, hematocrit, hemoglobin), fasting blood glucose, Hb1c, insulinemia, lipid profile (total cholesterol, c-HDL, c-LDL, triglycerides), kidney function (serum creatinine, creatinine clearance, glomerular filtration), nitrogen balance (urea, uric acid), thyroid profile (TSH, T4) and ionogram (Na, K, Cl, Ca, Mg)

The pre-inclusion blood test will also include liver function tests as the first screening of hepatic steatosis:

- GOT
- GPT
- Gamma-GT
- Bilirubin
- Albumin
- Prothrombin time
- Ferritin
- Alkaline phosphatase.

In addition, the patients will be informed about the study through the patient information sheet (Attachment 1) and they will be provided with an informed consent (Attachment 2).

At the baseline visit (day 0). The results of the additional tests (blood tests) will be verified to complete the inclusion/exclusion criteria.

Liver function data will be reviewed. Patients with one or more of the following conditions will be considered as suspicious of hepatic steatosis:

- GPT/GOT ratio over 1
- Gamma-GT and alkaline phosphatase increased twice to three times the normal levels
- High ferritin
- Normal bilirubin and albumin in the presence of any of the above changes

The informed consent will be signed and randomized. The corresponding diet will be scheduled depending on the treatment group (VLCK diet group or control group) and the physical exercise program. Patient demographics (sex, age, weight, height, comorbidities and medication) will be recorded. Anthropometric data (weight, BMI, waist circumference) will be recorded. Fat infiltration into liver and visceral fat will be scanned by MRI and hepatic stiffness will be assessed by MR Elastography. The salivary cortisol levels will also be tested.

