Control visit at month 2 or at the end of the ketogenic stage: For patients in the VLCK diet group, as soon as the patient loses 80% of the excess weight or within 2 months of treatment, just before moving to phase 3, the patient will undergo a new control. In the case of the control group, this visit will take place at month 2 of the hypocaloric diet.

The patient will undergo a new MRI and MR Elastography. The salivary cortisol levels will also be tested. Anthropometric data are recorded, the patient undergoes a complete blood test including liver function (GOT, GPT, GammaGT, bilirubin, albumin, prothrombin time, ferritin, alkaline phosphatase) and the potential occurrence of adverse effects will be recorded.

Visit at month 6 At month 6 of the study, a new control will be performed, evaluating hepatic steatosis and visceral fat using MRI and liver stiffness using MR Elastography. The salivary cortisol levels will also be tested. A complete blood test including liver function (GOT, GPT, GammaGT, bilirubin, albumin, prothrombin time, ferritin, alkaline phosphatase) will be required and the anthropometric data, the treatment phase, the blood test results and the potential occurrence of adverse effects will be recorded.

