10.2 Analysis of objectives

For the analysis of the primary objective and the secondary objectives, the differences between visits and between groups will be studied for the changes in the ratio between liver fat and the degree of steatosis (measured by MRI), changes in the degree of liver stiffness, changes in cortisol levels in saliva, weight changes, BMI and waist circumference, and changes in the amount of visceral fat among visits. The qualitative variables will be compared using Fisher's exact test, and the quantitative variables will be compared by means of the Student's t test for paired data. If the conditions to apply the Student's t test are not met, we will use the non-parametric Mann-Whitney U test. In the case of comparing paired data, we will use the tests described above, in their version for comparing this type of data.

The Pearson correlation coefficient or Spearman's correlation coefficient if the application conditions are not met will be used to study the following: the association between reduction of hepatic steatosis and weight loss and loss of visceral fat; the association between hepatic steatosis and liver stiffness; and the association between adrenal gland size and salivary cortisol levels with weight changes, BMI, hepatic steatosis and visceral fat.

For all tests, the significance level will be set at $p < 0.05$.

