13 PRACTICAL CONSIDERATIONS

13.1 Workplan

The investigators will be in charge of recruiting patients. Once the patients have confirmed their willingness to participate in the study, the investigator should verify if they meet the inclusion/exclusion criteria of this study. If they are eligible, they will be requested the additional tests (blood test with liver function) and will be informed on every issue of the study through the Patient Information Sheet (Attachment 1).

At the baseline visit, once the complementary tests have been reviewed and verified to meet inclusion criteria, the physician must confirm that the patient agrees to participate in the study and obtain the patient's signature of the Informed Consent (Attachment 2). Upon signing, the investigator will verify the assigned group according to the randomization list.

At this baseline visit, the physician should request MRI and MR Elastography to assess the degree of hepatic steatosis, the amount of visceral fat and liver stiffness. The physician will also perform the first salivary cortisol test on the patient. Also, he should record the clinical data requested in the Data Collection Notebook and schedule the treatment.

During the weight loss treatment, patients in the study group will be monitored by the investigator fortnightly during the protein diet (Ketogenic Active Stage), although at these additional visits no data are expected to be collected for the study. Upon completion of the first two months of follow-up, the study group will end the ketogenic stage and from that moment on, the patients will be controlled outside the center by dietitians specialized in the Pronokal® Method. Patients in the control group (hypocaloric diet) will undergo controls at the center monthly, although data will only be recorded in the visits arranged in this protocol (screening, baseline, month2 and month 6).

At the moment the patient completes the two months of follow-up, the data requested in the DCN will be recorded, the salivary cortisol test will be performed and an MRI and a MR Elastography will be requested.

The investigator, apart from monthly visits or any additional visits deemed necessary, will have an appointment with the patient at month 6 of treatment for a new clinical assessment, will record the anthropometric data, and request a Control MRI and MR Elastography.

At the end of the 6-month follow-up, the study will be completed.

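### Section 10.2 names no analysis set or missing-scan method, so MRI comparisons can use at most patients scanned at baseline and that visit; section 7.7 leaves dropout status unclear

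*Combined protocol and SAP*

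**What the plan says.** - **Analysis (10.2).** For the primary and secondary objectives, "the differences between visits and between groups will be studied". The outcomes are MRI liver fat and visceral fat, stiffness, salivary cortisol, weight, BMI and waist circumference. The tests are Student's t, Mann-Whitney U and Fisher's exact test, at p < 0.05. Neither 10.1 nor 10.2 names an analysis set or says what happens when a scan is missing.
- **Dropouts (7.7).** Dropouts are "Patients who do not attend the control visits and/or have not undergone at least two MRIs", the two MRIs being "baseline and control after the end of ketosis or at month 6".
- **Endpoints (9.1.3).** Liver fat, visceral fat and weight each have a change to month 2 (or the end of ketosis) and a second change "between the baseline visit and the control visit at month 6 of treatment".
- **Visits (9.2.1).** One follow-up visit is headed "Control visit at month 2 or at the end of the ketogenic stage". Section 9.1.3 also calls the month-6 visit a control visit. The flow chart (9.2.2) schedules MRI at baseline, month 2 and month 6 for all patients.
- **Discontinuation (13.1, last paragraph).** The investigator submits the visit sheets and records the reason. The text does not say whether later scheduled scans are still sought.
- **Size (7.4, 7.5).** 20 patients per arm, described as an exploratory pilot, with no dropout allowance.

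**The concern.** A change score needs two measurements, and the named tests cannot use a patient who lacks one. With no other rule, each comparison falls back on whoever happens to have both values. For the MRI outcomes that means a baseline scan plus that visit's scan. For weight, BMI, waist and cortisol it means that visit's measurement.

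Two things are at stake. If patients doing poorly are lost more from one arm than the other, two equally effective diets can look different, in either direction. And a change of patients between month 2 and month 6 could be read as a change in the diet effect.

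Section 7.7 does not settle who counts, so two analysts could classify the same patient differently after seeing the data.

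**Working it through.** **1. Readings of 7.7.** All patients below have a baseline scan.

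| Pattern | Any missed control visit counts | Only the two-MRI test counts | Both conditions required |
|---|---|---|---|
| Scanned at month 2, misses month-6 visit | dropout | not a dropout | not a dropout |
| Misses month-2 visit, scanned at month 6 | dropout | not a dropout | not a dropout |
| Attends both visits, no follow-up scan | dropout | dropout | not a dropout |

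Under every reading, the first two patients can supply a change score at one visit only.

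**2. How many patients could differ between visits.** Assume 5% of scans missing at month 2 and 10% at month 6.
- Independent misses: 40 × (0.05 × 0.90 + 0.10 × 0.95) = 40 × 0.14 = 5.6 patients in only one comparison.
- Permanent loss: 40 × (0.10 − 0.05) = 2 patients.

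**3. Bias of a single comparison.** From the protocol: 20 per arm. Assumed: no true difference, change scores with SD 1, two-sided 5% test, and loss of the patients with the lowest score on a dropout tendency that correlates ρ with outcome. Let m(k) be the mean shift of the remaining patients when exactly the k worst of 20 are lost. By simulation m(2) = 0.182, m(4) = 0.332 and m(6) = 0.475. Then

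bias = ρ × [m(lost in arm A) − m(lost in arm B)].

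The false-positive column comes from 60,000 simulated null trials per case.

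| Lost | ρ | Formula | Simulated bias | False positives |
|---|---|---|---|---|
| 4 vs 2 | 0.5 | 0.5 × (0.332 − 0.182) = 0.075 | 0.076 SD | 6.1% |
| 6 vs 2 | 0.5 | 0.5 × (0.475 − 0.182) = 0.147 | 0.147 SD | 7.7% |
| 4 vs 0 | 0.5 | 0.5 × 0.332 = 0.166 | 0.169 SD | 8.0% |
| 6 vs 0 | 0.5 | 0.5 × 0.475 = 0.238 | 0.238 SD | 10.7% |
| 4 vs 4 | same in both arms | 0 | 0.00 SD | – |
| one arm only | 0 | 0 | 0.00 SD | 5% |

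Standard error with 16 vs 18 analysed: √(1/16 + 1/18) = 0.344 SD. With 14 vs 20: √(1/14 + 1/20) = 0.348 SD. The lower case is thus a shift of 0.076 / 0.344 = 0.22 standard errors, the upper 0.238 / 0.348 = 0.68.

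**4. What a repeated-measures model can recover.** Assume 4 or 6 of 20 lost from one arm after the month-2 scan, ρ of 0.5 or 1, and a correlation r of 0.5 or 0.7 between the month-2 and month-6 changes.
- *Loss depends on the observed month-2 change.* Completer bias at month 6 is ρ × r × m(k), from 0.5 × 0.5 × 0.332 = 0.083 to 1 × 0.7 × 0.475 = 0.333 SD. The likelihood estimate is within 0.003 SD of zero in simulation.
- *Loss depends on the unseen month-6 change.* Completer bias is ρ × m(k), from 0.166 to 0.475 SD (about 0.17 to 0.48). The likelihood estimate keeps about 0.09 to 0.40 SD in simulation, so the model reduces this bias without removing it.

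**The case against.** **What stands.** The study is an exploratory pilot, and every loss rate and mechanism above is assumed. In the moderate case the bias is small beside the standard error and the false-positive rate hardly moves; reaching 11% takes 30% loss from one arm and none from the other. Reasons for discontinuation are already collected, and the flow chart has a dropout entry at both follow-up visits. Section 7.7 contains no diet-adherence criterion, so stopping the diet is not in itself dropout. This lowers the priority. It does not supply the missing rule, and 10.2 still tests between groups.

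**Stronger readings that the documents do not support.**
- *Dropouts are removed from the analysis.* Section 7.7 defines them but does not say so. If they were removed, the usable set could be narrower still; the wording has no demonstrated effect on the analysis.
- *Section 7.7 contradicts the endpoints.* Accepting baseline plus either follow-up MRI is not a contradiction, since a dropout definition need not require every endpoint visit. It also keeps partly observed patients, which is desirable.
- *Every comparison depends on scans.* Weight, BMI, waist and cortisol do not.
- *The arms are followed unequally, so loss will be unequal.* The text is mixed. Section 9.2.1 says "The patients will be visited monthly and data will be recorded on 4 occasions". Section 13.1 has fortnightly monitoring of the ketogenic arm during ketosis, after which "the patients will be controlled outside the center by dietitians specialized in the Pronokal® Method", yet it also has the investigator seeing the patient at month 6 "apart from monthly visits or any additional visits deemed necessary". Unequal loss is possible, not shown.
- *Only continued scanning helps when loss depends on the unseen result.* The model also helps, in part.

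**Conclusion.** The concern holds in this limited form: the plan has no analysis set and no missing-scan method, the MRI comparisons can use at most patients with baseline plus that visit's scan, and 7.7 leaves it open whether one missed control visit makes a dropout. That the comparisons reduce to available cases is an inference from the named tests, not a stated rule.

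The plausible size is a bias of about 0.08 to 0.24 SD with false positives of 6% to 11%, on assumed unequal, outcome-related loss. Without such loss there is no bias. Low to moderate priority: worth correcting because it is cheap and can be settled before the data are seen, not because the trial is shown to be biased.

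**What to change.** 1. **Section 10.2.** Make the main between-diet comparison by assigned group, using a baseline-adjusted repeated-measures model (arm, visit, arm-by-visit, baseline value). Include every randomised patient with a baseline value and at least one follow-up value. State that it removes bias when loss depends on observed values, only reduces it when loss depends on the unseen month-6 result, and gains nothing from patients with no follow-up value. Keep a two-sample t or Mann-Whitney test on change as a supportive check.
2. **Sections 7.7 and 13.1.** Say whether missing one control visit makes a patient a dropout. Still invite every patient who has not withdrawn consent to the month-2 and month-6 MRIs already scheduled, including those who missed visits or stopped the diet.
3. **Reporting and sensitivity.** Report missing scans and reasons by arm and visit. Add one sensitivity analysis: multiply impute missing changes by arm from baseline and any observed visit, then worsen the imputed values by fixed amounts (for example 0.5 and 1 SD) in each arm in turn.

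Cost: protocol and SAP wording, a little more follow-up and analysis work, and a possibly less favourable estimate. No scan is added to the schedule.

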8 TREATMENT DESCRIPTION

8.1 Weight Loss Program: PronoKal® Method

All patients in the study group will undergo the same standardized weight loss program (PronoKal® Method) with progressive diet based on commercial high-biological-value protein preparations, dietary supplements, physical exercise plan and emotional support, structured in 3 stages: active stage, food re-education stage and maintenance stage

80% of target weight loss			20% of target weight loss		Long-term maintenance of weight loss
Multidisciplinary team (Dietary counseling/physical activity/psychological support)					
Weight Loss Moment					My New Lifestyle Moment
Step 1	Step 2	Step 3	Step 4	Step 5	
Low-fat ketogenic diet (very low-calorie-ketogenic diet) 600-730 kcal/day			Low calorie diet (800-1500 kcal/day)		Controlled diet adapted
Supplementation Vitamins, trace elements OMEGA BALANCE: 700 DHA/500 EPA			Supplementation Vitamins, trace elements DHA VITA: 500 DHA/100 EPA		DHA VITA: 500 DHA/100 EPA

a) Treatment schedule

Active stage: The diet will consist of a protein diet, ie a very low-calorie ketogenic diet (VLCK diet) (between 650 and 730 kcal/day) based on PronoKal® commercial preparations and low-glycemic-index vegetables. Patients will start with 5 commercial

preparations a day. Two of them will be replaced progressively by natural proteins (meat or fish). This active stage will be maintained for 2 months.

- Phase 1: Protein diet of 600 kcal/ day (with 5 PronoKal® products and low-glycemic-index vegetables) + Nutritional supplements (vitamins and trace elements) + Cardiovascular physical exercise + Emotional support.
- Phase 2a: Protein diet of 680 kcal/day (with 4 PronoKal® products, a high-protein food [meat or fish] and low-glycemic-index vegetables) + Nutritional supplements (vitamins and trace elements) + Cardiovascular physical exercise + Emotional support.+ Soporte emocional.
- Phase 2b: Protein diet of 780 kcal / day (with 3 PronoKal® products, two high-protein foods [meat or fish] and low-glycemic-index vegetables) + Nutritional supplements (vitamins and trace elements) + Cardiovascular physical exercise + Emotional support.

Patients will remain in Phase 1 until they have lost 40% of the excess weight or the target weight to be lost. Subsequently, they go on to Phase 2a until they have lost 60% of the excess weight and then to Phase 2b until they have lost 80% of the excess weight.

For this study, patients will leave the active Ketogenic Stage within 2 months of treatment, even if they have failed to achieve 80% of the weight loss goal.

Phase of physiological adaptation: Progressive introduction of natural foods and maintaining the intake of 2 commercial preparations per day, with a progressive increase in calorie intake up to 1300-1500 kcal/day and an increased supply of carbohydrates. The diet will be accompanied by with cardiovascular physical exercise and emotional support. The length of the food re-education stage will be 4 months.

Maintenance stage: Upon completion of dietary re-education, the patient will go on a balanced diet of 1500-2200 kcal/day, along with cardiovascular physical exercise and emotional support, until completing the 2-year follow-up.

8.2 Hypocaloric diet

Balanced hypocaloric diet (caloric intake 10% below basal metabolic rate).

The diet will also be accompanied by physical exercise.

9 STUDY PROCEDURES AND OUTCOME MEASURES

9.1 Outcome measures

9.1.1 *Primary variables*

- Liver fatty infiltration, measured by a MRI technique of fat liver quantification (Ideal IQ**).
- Visceral fat, measured by the area in squared centimeters at the level of the 3rd vertebrae, using MRI technique.

9.1.2 *Secondary variable*

- Liver stiffness detected by MR Elastography
- Adrenal gland linear measurement
- Body weight
- Salivary cortisol levels

9.1.3 *End points*

- Reduction of fat infiltration into the liver between the baseline visit and 2 months (or end of the ketosis stage) and between the baseline visit and the control visit at month 6 of treatment.
- Visceral fat reduction between the baseline visit and 2 months (or end of the ketosis stage) and between the baseline visit and the control visit at month 6 of treatment.
- Correlation between degree of liver fat infiltration and liver stiffness
- Correlation between adrenal gland size and BMI, visceral fat and liver steatosis.
- Correlation between salivary cortisol levels and BMI, visceral fat and liver steatosis.
- Weight loss between the baseline visit and 2 months (or end of the ketosis stage) and between the baseline visit and the control visit at month 6 of treatment.

9.2 Study procedures

9.2.1 *Follow-up of patients*

The patient follow-up will be 6 months. The patients will be visited monthly and data will be recorded on 4 occasions: pre-inclusion, baseline visit, final visit Active stage (end of ketosis) and visit at month 6.

Patients will be included after verifying the inclusion and exclusion criteria and after obtaining the signed informed consent.

Screening visit (day -15). In this visit, the patient's medical history will be assessed and a complete blood test will be required to verify the inclusion/exclusion criteria: complete blood count (red blood cells, leukocytes, neutrophils, hematocrit, hemoglobin), fasting blood glucose, Hb1c, insulinemia, lipid profile (total cholesterol, c-HDL, c-LDL, triglycerides), kidney function (serum creatinine, creatinine clearance, glomerular filtration), nitrogen balance (urea, uric acid), thyroid profile (TSH, T4) and ionogram (Na, K, Cl, Ca, Mg)

The pre-inclusion blood test will also include liver function tests as the first screening of hepatic steatosis:

- GOT
- GPT
- Gamma-GT
- Bilirubin
- Albumin
- Prothrombin time
- Ferritin
- Alkaline phosphatase.

In addition, the patients will be informed about the study through the patient information sheet (Attachment 1) and they will be provided with an informed consent (Attachment 2).

At the baseline visit (day 0). The results of the additional tests (blood tests) will be verified to complete the inclusion/exclusion criteria.

Liver function data will be reviewed. Patients with one or more of the following conditions will be considered as suspicious of hepatic steatosis:

- GPT/GOT ratio over 1
- Gamma-GT and alkaline phosphatase increased twice to three times the normal levels
- High ferritin
- Normal bilirubin and albumin in the presence of any of the above changes

The informed consent will be signed and randomized. The corresponding diet will be scheduled depending on the treatment group (VLCK diet group or control group) and the physical exercise program. Patient demographics (sex, age, weight, height, comorbidities and medication) will be recorded. Anthropometric data (weight, BMI, waist circumference) will be recorded. Fat infiltration into liver and visceral fat will be scanned by MRI and hepatic stiffness will be assessed by MR Elastography. The salivary cortisol levels will also be tested.

Control visit at month 2 or at the end of the ketogenic stage: For patients in the VLCK diet group, as soon as the patient loses 80% of the excess weight or within 2 months of treatment, just before moving to phase 3, the patient will undergo a new control. In the case of the control group, this visit will take place at month 2 of the hypocaloric diet.

The patient will undergo a new MRI and MR Elastography. The salivary cortisol levels will also be tested. Anthropometric data are recorded, the patient undergoes a complete blood test including liver function (GOT, GPT, GammaGT, bilirubin, albumin, prothrombin time, ferritin, alkaline phosphatase) and the potential occurrence of adverse effects will be recorded.

Visit at month 6 At month 6 of the study, a new control will be performed, evaluating hepatic steatosis and visceral fat using MRI and liver stiffness using MR Elastography. The salivary cortisol levels will also be tested. A complete blood test including liver function (GOT, GPT, GammaGT, bilirubin, albumin, prothrombin time, ferritin, alkaline phosphatase) will be required and the anthropometric data, the treatment phase, the blood test results and the potential occurrence of adverse effects will be recorded.

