7 SUBJECT SELECTION

7.1 Study population

Obese patients of either sex with BMI over 30 kg/m², who agree to participate in the study.

7.2 Inclusion criteria:

- Patients of either sex, older than 18 years
-

-
- Obese patients with BMI equal or over 30kg/m²
 - Patients who agree to participate and sign the Informed Consent

7.3 Exclusion criteria:

- Pregnant or lactating women.
 - Patients weighing over 140 kg (by limitation of the MRI device)
 - Patients on anti-obesity drugs (eg, sibutramine, orlistat and liraglutide) or weight-interfering medications (eg, topiramate). In such cases a wash out period of 3 months is required.
 - Patients with alcohol intake > 20 g/day in women and > 30 g/day in men.
 - Patients with liver failure or with pathologies that may affect the liver
 - Patients with other causes of liver steatosis: chronic viral hepatitis and/or drug intake (corticosteroids, estrogens, NSAIDs, calcium antagonists, amiodarone, tamoxifen, tetracyclines, chloroquine, antiretrovirals, perhexiline).
 - Patients with eating disorders.
 - Patients with any psychiatric disorder (eg schizophrenia, bipolar disorder, substance abuse, severe depression).
 - Patients receiving dicumarinic anticoagulants (Sintrom®).
 - Patients taking corticosteroids.
 - Patients with severe kidney failure (gfr <30).
 - Patients with type 1 and type 2 diabetes mellitus.
 - Patients with hemopathies, including coagulation disorders
 - Patients with cardiovascular or cerebrovascular disease (of heart rate disorders, recent infarction [$<6m$], unstable angina, decompensated heart failure, recent stroke [$<6m$]).
 - Patients in acute attack of gout.
 - Patients with renal lithiasis verified by ultrasound.
 - Patients with cholelithiasis verified by ultrasound.
 - Patients with electrolyte imbalance, according to medical criteria.
 - Patients with orthostatic hypotension.
 - Patients with cancer or history of cancer who have not been discharged from oncology
 - Patients who are not expected to attend follow-up visits
-

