9.2.2 Flow chart

	Pre-study	Onset	Visit at month 2 (end of ketosis)	Visit at month 6 (Final visit)
Review of inclusion and exclusion criteria.	X	X		
General blood test with liver function	X		X	X
Patient information	X			
Informed consent		X		
Comorbidities and medication		X	X	X
Anthropometric data (weight, BMI, WC)	X	X	X	X
MRI + MR Elastography		X	X	X
Salivary cortisol test		X	X	X
Adverse reactions			X	X
Drop outs and end of study			X	X

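### No specified test supports the exclusions for pregnancy and chronic viral hepatitis; both rest on history and investigator judgement

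*Combined protocol and SAP*

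**What the plan says.** The exclusion list in section 7.3 opens with "Pregnant or lactating women" and later rules out "Patients with other causes of liver steatosis: chronic viral hepatitis and/or drug intake", followed by a list of drugs. A separate item excludes liver failure and other conditions that may affect the liver.

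Section 9.2.1 gives the means of checking eligibility about two weeks before baseline (day -15): the history is reviewed, and "a complete blood test will be required to verify the inclusion/exclusion criteria". The content of the test follows in detail, beginning with "complete blood count (red blood cells, leukocytes, neutrophils, hematocrit, hemoglobin), fasting blood glucose, Hb1c, insulinemia, lipid profile" and going on to kidney function, urea and uric acid, thyroid hormones and individual electrolytes. A liver panel is added, with its purpose stated: "The pre-inclusion blood test will also include liver function tests as the first screening of hepatic steatosis". It comprises GOT, GPT, Gamma-GT, bilirubin, albumin, prothrombin time, ferritin and alkaline phosphatase.

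At the baseline visit (day 0) eligibility is completed on those same results, consent is signed and the patient is randomised. The flow chart in 9.2.2 has one blood-test row, "General blood test with liver function", marked before the study and at months 2 and 6. The workplan in 13.1 likewise names only a blood test with liver function.

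**The concern.** The plan presents its blood test as a means of verifying the criteria and itemises it down to single electrolytes, yet two exclusions that a routine assay could check have no assay. A site that follows the list will find hepatitis or pregnancy only if the patient already knows of it or the investigator suspects it.

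The stakes differ. For pregnancy the issue is safety: women over 18 are eligible, both diets (8.1 and 8.2) restrict calories, and the protocol's own exclusion would depend on what the patient knows and reports. For hepatitis the issue is measurement. Section 7.3 itself treats chronic viral hepatitis as a competing cause of steatosis. MRI liver fat is a primary variable (9.1.1), stiffness is a secondary variable (9.1.2), and their correlation is a listed end point (9.1.3) and a secondary aim (5.2).

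**Working it through.** The plan gives no figure to reproduce. The check has three steps.

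**1. Exclusions against procedures**

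| Where a test could be specified | Hepatitis B/C marker | Pregnancy test |
|---|---|---|
| Screening panel, 9.2.1 | none | none |
| Liver panel, 9.2.1 | none | none |
| Baseline visit, 9.2.1 | none | none |
| Flow chart, 9.2.2 | none | none |
| Workplan, 13.1 | none | none |

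So 0 of the 2 exclusions is backed by a specified test. What remains is the medical history at screening, the review of criteria before the study and at onset (9.2.2), and the investigator's judgement. These can find known hepatitis, known pregnancy and lactation.

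**2. How likely is an undiagnosed carrier?**

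Inputs: n = 40 (section 7.4); p = the share of undiagnosed carriers among candidates who pass every other check. The documents do not give p, so 0.5% to 2% is an assumed range. With independent patients, P(at least one) = 1 - (1 - p)^40.

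- p = 0.005: 1 - 0.995^40 = 0.18
- p = 0.01: 1 - 0.99^40 = 0.33
- p = 0.02: 1 - 0.98^40 = 0.55

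The expected number of carriers is 40p = 0.2, 0.4 or 0.8. These are chances of inclusion, not of a distorted result.

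**3. What could one such patient do?**

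*Comparison of arms.* One patient is 1/20 = 5% of an arm and 1/40 = 2.5% of the trial. If that patient's change in liver fat is off by d, the arm mean moves by d/20. Randomisation makes either arm equally likely to receive the patient, so the expected shift in the difference between arms from this source of misclassification is zero and the effect is noise.

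*Correlation of liver fat and stiffness.* Assume 39 patients with both variables standardised and a true r of 0.3, plus one patient with stiffness 4 SD high. The expected sums over the 39 are 38 for each variable and 38 × 0.3 = 11.4 for the cross-product. An added point at (x, y) contributes (39/40)x², (39/40)y² and (39/40)xy.

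- Liver fat 2 SD high: r ≈ (11.4 + 7.8) / √[(38 + 3.9)(38 + 15.6)] = 19.2 / 47.4 ≈ 0.41
- Liver fat 1 SD low: r ≈ (11.4 - 3.9) / √[(38 + 0.975)(38 + 15.6)] = 7.5 / 45.7 ≈ 0.16

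Under these assumptions one extreme patient moves r from 0.30 to about 0.41 or 0.16: a material change in either direction, though the patient does not dominate the coefficient. The size of the outlier and the true r are assumptions. That viral hepatitis can raise stiffness is general clinical knowledge, not something the documents state.

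**The case against.** The case on the other side narrows the point considerably.

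- A reader might infer that the two exclusions cannot be verified at all. The documents do not support that: the sentence that introduces the blood test also names the medical history, and the criteria are reviewed twice.
- A reader might infer that abnormal liver tests lead a hepatitis carrier to be labelled as suspected fatty liver and so randomised. Section 9.2.1 does list a GPT/GOT ratio over 1 among its signs of suspected steatosis, but that is a ratio, not raised transaminases; steatosis is not an inclusion criterion; and no action follows from the flag. An investigator who sees abnormal results may still apply the broader exclusion for conditions affecting the liver. Equally, nothing in the plan tells the investigator to look for a viral cause.
- A reader might infer that the primary comparison is contaminated or biased. The primary end points are changes from baseline between randomised arms. A stable viral contribution largely cancels within a patient and is balanced between arms on average.
- Other exclusions, such as psychiatric or eating disorders, also rest on history, and how much to test in a 40-patient pilot is partly a matter of judgement. That is fair. These two differ in that they can be unknown to the patient and can be settled by routine assays at visits already scheduled.
- Section 10.2 allows Spearman's coefficient, which limits the pull of an outlier, but only if the conditions for Pearson are not met. It plans no check for influential patients.
- The Data Collection Notebook and attachments were not available for this review, so a test named only there cannot be ruled out. The protocol would still need to state it.

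**Conclusion.** The point holds in this form: no test specified in the protocol supports the pregnancy or viral hepatitis exclusion. Both depend on history and judgement, and undiagnosed hepatitis or unrecognised pregnancy would be missed.

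The pregnancy part is the stronger. It concerns participant protection and needs no calculation. The hepatitis part is smaller: added noise in liver fat, and a possible distortion of one secondary correlation. It is not a source of systematic bias between the arms. The 18%, 33% and 55% are illustrations that rest wholly on the assumed prevalences; if history or abnormal liver tests remove some carriers, the effective p and these chances fall. This is a cheap improvement that should be made, and the validity of the trial does not turn on it.

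**What to change.** Amend 9.2.1, the flow chart in 9.2.2 and the workplan in 13.1 together:

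1. Add HBsAg and anti-HCV for all patients to the screening blood test.
2. Move written consent to the screening visit, before the sample is taken. At present consent is signed only at day 0, so the added serology would otherwise precede it.
3. Add a pregnancy test for women of child-bearing potential at the baseline visit, after consent and before randomisation. A single test at day -15 would leave the interval to randomisation uncovered.
4. State that all these results must be available before the patient is randomised.

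If the tests already stand in the Data Collection Notebook, carry them into these sections. At the least, the protocol should say how each of the two exclusions is ascertained.

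Cost: two routine assays per screened patient on blood already drawn, and one pregnancy test for each woman concerned at an existing visit. The downsides are a small laboratory cost, consent brought forward to screening, and possibly one or two more screen failures. No extra visit is needed.
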